1. BACKGROUND AND PROJECT RATIONALE

In 2013 the QualiCCare association was founded, the purpose of which, according to the statutes, is to develop concrete and pragmatic measures for the treatment of the chronically ill in the extended primary care through the interprofessional cooperation of all stakeholders. This involves coordination with the national strategies in the field of chronic diseases (NCD, CVSD, etc.), as well as a continuous review of the measures developed in the "real-life" setting, i.e. in primary care.

Based on international guidelines, the QualiCCare 2011-2013 project identified essential treatment elements for which there is potential for improvement in Switzerland compared with best practice examples. Four priorities were identified for diabetes mellitus type 2: (1) screening and diagnosis, (2) self-management training, (3) drug therapy of diabetes and co-risk factors, and (4) control and treatment of macrovascular and microvascular complications. Specific and pragmatic measures have been developed to improve treatment outcomes. Based on the NCQA recommendations (National Council Quality Assurance) and a best-practice comparison with other countries, developed as part of the QualiCCare project 2011-2013, the Swiss Society for Diabetology and Endocrinology (SGED) developed adapted "criteria for "good" disease management diabetes in primary care" (hereinafter "criteria") for Switzerland. The quality of care for patients with type 2 diabetes can be evaluated by calculating a score determined during the application of the criteria. In two pilot projects, the criteria were followed in a multi-year comparison:

I. Pilot project I: all type 2 diabetes patients of a single primary care practice with several doctors over 3 years;

II. pilot project II: all type 2 diabetes patients in the Chronic Care Management Program in 5 group practices over 2 years.

The aim of the Diabetes Project III is to establish the above-mentioned score in different practice infrastructures. The aim is to record the effect of the score on the quality of treatment and to evaluate its suitability for practical use. The score criteria will additionally include influenza vaccination as an important prevention measure and the drug therapy (oral antidiabetics and/or insulin, antihypertensives, and statins) in order to determine possible comorbidities based on the medication.

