2.4 Statistics and methodology

Statistical evaluation concept:

Primary endpoint:

Comparison of score baseline vs. 12 months using paired t-test.

Secondary endpoints:

Comparison of score changes between individual practices and practice networks using unpaired t-test.

Evaluation of the evaluation forms with regard to practical suitability and software by means of descriptive statistics.

In the previous two pilot studies, a measurable improvement in treatment quality could be measured in one and five primary care practices, respectively, with an increase in the score to 58 + 20 points. In order to achieve the goal of a relevant improvement of the overall score by a total of 10 points (from 56 to 66 points), 27 centres must be recruited with a significance level of 0.05 and a power of 80% (1). At a dropout rate of 10%, we will recruit 30 centers.

Methodology

Information of the primary care practices regarding the background and goal of the project by means of a letter and informative documentation.

Recruitment of primary care practices, divided into three different practice organisations (individual practices and group practices run on a private basis and with financial autonomy, as well as forms of joint practices with employed physicians without financial autonomy).

A signed contract between QualiCCare and participating primary care practices regulates the collaboration.

Procedure:

A baseline documentation takes place retrospectively from the training/workshop for the past 12 months, and a second, prospective documentation of the treatment is done during the following 12 months.

Training of the participating GPs and practice coordinator on the project including evaluation software, data entry and background to the criteria.

Documentation of the treatment quality of all patients with diabetes mellitus type 2 in a practice structure that meets the inclusion criteria according to the score criteria (baseline).

After 12 months, the treatment quality of the included patients with diabetes type 2 is recorded again using the same score.

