2.5 Handling of missing data and dropouts

Dropouts are also recorded because it is assumed that the treatment quality (score) of the collective is not changed.

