3.3 Study procedures

The duration of the project is 3 years, including recruitment and publication, i.e. from December 2017 until the end of 2020. After the recruitment of the primary care practices, training will take place in the form of an interprofessional workshop for the GPs and the responsible practice assistants on application and background of the score, as well as on its documentation in the tool. After the workshop, the practices will retrospectively create the baseline from their patient files. For the prospective data collection, the score criteria are recorded each time the patient visits the practice. In order to support the interprofessional cooperation with actors outside the GP's practice, the diabetes passport, revised by QualiCCare and distributed by Diabetesschweiz, can be used. Over a period of 12 months, all score criteria per patient must be recorded in the practice (primary endpoint). The project manager evaluates the difference between retrospective baseline and prospective score criteria documentation. The practices receive the evaluation of their practice and must answer a questionnaire to assess the recording tool with regard to practicability and suitability for practice. The results of the study will be published.

A selection bias may occur by not considering patients with difficult psychosocial problems, but since the patient collective is relevant and not the individual patient, this bias is not significant.

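### The primary test compares a retrospective, file-based baseline with prospective recording, and nothing planned separates fuller recording from the better treatment quality claimed in 2.1

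*Combined protocol and SAP*

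**What the plan says.** Section 2.4 makes the primary analysis a paired t-test of the score at baseline against 12 months. Its procedure reads "A baseline documentation takes place retrospectively from the training/workshop for the past 12 months, and a second, prospective documentation of the treatment is done" over the year that follows. Section 3.3 names the sources. For the baseline: "After the workshop, the practices will retrospectively create the baseline from their patient files". For follow-up: "For the prospective data collection, the score criteria are recorded each time the patient visits the practice". It adds a completeness requirement that applies to the follow-up year: "Over a period of 12 months, all score criteria per patient must be recorded in the practice (primary endpoint").

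The instrument is held constant: after 12 months "the treatment quality of the included patients with diabetes type 2 is recorded again using the same score" (section 2.4). GPs and practice staff are trained before both documentations.

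Section 2.1 defines treatment quality through an improvement of the score, and section 2.2 sets the primary endpoint as the change in score after using the documentation method. Section 2.3 states that there is no control group. Section 2.5, on missing data, deals with patients who leave: "Dropouts are also recorded because it is assumed that the treatment quality (score) of the collective is not changed". It does not say how a criterion with no entry is scored. Section 6.1 rules out monitoring and provides training and a descriptive plausibility check. The only bias that section 3.3 discusses is selection.

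**The concern.** The two halves of each pair are ascertained differently. The baseline year lies before the workshop, so its files were written by practices that had not yet been trained on the criteria. Training before abstraction helps staff find what is in the file, but it cannot recover care that was given and never noted. In the follow-up year the criteria are entered at each visit, with an instruction to record all of them.

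If capture is better in the second year, the score can rise with no change in care. The paired t-test takes the whole difference as its estimate, and no other planned element would show which part is recording. At stake is the conclusion, not the arithmetic of the test: a significant primary result would be reported under 2.1 as better treatment quality when the comparison supports only a better documented score.

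**Working it through.** **Plan figures.** The relevant one is the target change, 66 − 56 = 10 points (sections 2.4 and 3.1). The centre numbers (27, and 27 / 0.90 = 30 after dropout) concern precision and do not bear on a bias. The documents give no capture rate, no share of points that depend on recording, and no scoring rule for an unrecorded criterion.

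**Side by side.**

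| | Baseline | Follow-up |
|---|---|---|
| Period | 12 months before the workshop | 12 months after |
| Source | existing patient files | criteria entered at each visit |
| Completeness requirement | none stated | all criteria per patient |
| Score | same | same |
| Staff trained when documenting | yes | yes |
| Staff trained when care was given | no | yes |

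**Purely illustrative model.** Every input except 56 is an assumption. Care is unchanged and an unrecorded criterion counts as unmet. Let f be the share of points for delivered care that depend on something being written down, and c0 and c1 the captured share of those points at baseline and follow-up. Then observed score = true score × [(1 − f) + f·c]. Starting from an observed baseline of 56:

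apparent rise = 56 × { [(1 − f) + f·c1] / [(1 − f) + f·c0] − 1 }

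Worked case, f = 0.5, c0 = 0.90, c1 = 1: 56 × (1 / 0.95 − 1) = 2.9 points.

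| Assumed f and c1 | c0 = 0.95 | c0 = 0.90 | c0 = 0.85 | Share of 10 points |
|---|---|---|---|---|
| f = 0.25, c1 = 1 | +0.7 | +1.4 | +2.2 | 7% to 22% |
| f = 0.5, c1 = 1 | +1.4 | +2.9 | +4.5 | 14% to 45% |
| f = 0.5, c1 = 0.95 | 0 | +1.5 | +3.0 | 0 to 30% |

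**Other directions.**
- If unrecorded criteria leave the denominator and are missing at random, the share of criteria met is unaffected on average and the artefact is 0.
- If follow-up capture is worse than baseline capture, the sign reverses. With f = 0.5, c0 = 0.95 and c1 = 0.90: 56 × (0.950 / 0.975 − 1) = −1.4 points.

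The result therefore turns on two things the documents do not give: the scoring rule and the completeness at each time.

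**The case against.** The strongest reply is that recording is the intervention. Section 2.2 defines the endpoint as the change after use of a method to document care, and section 1 treats the score as a way to evaluate quality of care. On that view 2.1 merely operationalises quality as the score. This stands in part: a rise in documented care is a legitimate finding, and 2.1 is a hypothesis, not a reporting rule. It does not remove the problem, because section 5.2 looks to better treatment of patients, and the comparison alone cannot show that.

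A second reply is that the criteria and their scoring come from the diabetology society and are not reproduced in the protocol, so a rule for unrecorded items may exist there. That also stands. It limits what can be said about size, and such a rule could simply be cited.

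A third is that an instruction to record everything is not proof that everything is recorded; entries can be missed at busy visits. This stands too, and is why the direction is left open.

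A reader might go further in three ways that the documents do not support:
- *That about 15% under-capture would explain the whole target.* The formula gives +9.9 points at c0 = 0.85 only if every point depends on recording (f = 1) and follow-up is complete. Nothing in the documents supports that combination.
- *That regression to the mean adds to the rise.* Section 3.1 takes all eligible patients, with no selection on a low score.
- *That drug therapy supplies a verifiable, point-earning criterion.* Section 1 says "The score criteria will additionally include influenza vaccination as an important prevention measure and the drug therapy", but gives identifying comorbidities as its purpose and does not say that it earns points.

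**Conclusion.** The concern holds as a limit on interpretation. The documents establish that ascertainment differs between the two times, that completeness may therefore differ, and that nothing planned separates fuller recording from better care, while 2.1 equates the score with treatment quality.

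They do not establish a bias of any given size or sign. Under the assumed capture rates it runs from 0 to a substantial part of the 10-point target (up to 45% with half the points dependent on recording). It is 0 under one plausible denominator rule, and it reverses if follow-up capture is the poorer. A reader might infer that an observed rise would be mainly an artefact; the documents do not support that. This is a cheap improvement to the plan. It does not invalidate the design.

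**What to change.** In section 2.4:
1. State one rule for scoring an unrecorded criterion and apply it at both times, citing the society's rule if there is one.
2. Report completeness for each criterion at baseline and at follow-up. If the tool cannot tell not recorded from not met, say so in the report.
3. Report the score change separately for criteria whose values already exist in the file as results (such as laboratory values, if they are scored) and for criteria that depend on an action being written down. Classify by type of criterion, in advance. No external verification is meant: section 6.1 excludes monitoring, and section 6.2 limits access to patient data to the physician and practice staff.

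In section 2.1, state that a rise confined to documentation-dependent criteria, or accompanied by a clear rise in completeness, will be reported as improved documented care and not as demonstrated improvement in treatment quality.

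The cost is a little more analysis of data already collected, two text edits, and possibly a narrower claim. The split helps to tell the explanations apart but cannot settle them, and the absence of a control group remains a separate limitation.

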2.5 Handling of missing data and dropouts

Dropouts are also recorded because it is assumed that the treatment quality (score) of the collective is not changed.

3. SUBJECTS AND STUDY PROCEDURES

3.1 Project population, inclusion and exclusion criteria

Reason for the number of patients:

In order to achieve the goal of a relevant improvement of the overall score by a total of 10 points (from 56 to 66 points), 27 centres must be recruited with a significance level of 0.05 and a power of 80%. The standard deviation of the total score in the individual practices is + 15, so that a patient population of > 50 patients per practice is necessary.

At a dropout rate of 10%, we will recruit 30 centers.

Inclusion and exclusion criteria:

Inclusion criteria:

All patients who have been diagnosed with type 2 diabetes mellitus according to their primary care provider, i.e. who have ever had HbA1c > 6.4% and/or are taking insulin and/or oral AD according to their patient dossier.

AND are at least 9 months in treatment with the same physician (in group practice in the same practice)

Exclusion:

Supervision <9 months in practice (change of practice, move, death, complete external supervision regarding DM, etc.)

Patients who do not agree to participate in the project

Patients for whom the doctor decides that they cannot participate in the project due to their illness (frailty, end of life).

All excluded patients will be anonymized and the reason for the exclusion will be stated. The excluded patients will not be considered for the evaluation.

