3.2 Recruitment, screening and informed consent procedure

The general practitioners will be invited to participate by post with a letter and information about QualiCCare and the project. There will be 10 practices per organisational structure. Each practice documents its diabetes patients based on their patient dossiers according to inclusion criteria. In order to participate in the study, patients will be informed about the study at the next follow-up and asked to sign a letter of consent to participate. A document will be available to the practices for patient information. Patients will be given sufficient time to decide whether to participate in the study.

The practice will receive CHF 50.00 per participating patient with documented score and free use of the diabetes management tool during the duration of the project. The medical services will be reimbursed according to usual tariff, Tarmed. In addition, the practice receives an evaluation of its practice performance compared to the overall collective.

The patient does not receive any financial compensation.

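### The primary paired t-test has no stated unit or allowance for clustering, although the sample size counts centres; a minor related point is that SD 15 alone does not give more than 50 patients per practice

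*Combined protocol and SAP*

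**What the plan says.** The sample size is stated in centres. Sections 2.4 and 3.1 both aim for a gain of 10 points (56 to 66), and 3.1 says "27 centres must be recruited with a significance level of 0.05 and a power of 80" percent. A 10% dropout rate raises 27 to 30 centres.

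The analysis in section 2.4 is one line: "Comparison of score baseline vs. 12 months using paired t-test". No unit, sidedness or SD of change is given, and clustering is not mentioned. Each practice contributes many patients, since the procedure calls for "Documentation of the treatment quality of all patients with diabetes mellitus type 2 in a practice structure" that meet the inclusion criteria.

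Section 3.3 points both ways on the unit. It ties the primary endpoint to criteria recorded for each patient over 12 months. Later, when it discusses selection bias, it says that the collective matters and the individual patient does not.

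On patients per practice, section 3.1 says "The standard deviation of the total score in the individual practices is + 15", and continues "so that a patient population of > 50 patients per practice is necessary". Section 2.4 gives a second spread-like figure from the pilot studies, "with an increase in the score to 58 + 20 points", and does not say what the 20 is.

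**The concern.** Two analysts could follow section 2.4 faithfully and report different primary results, one from 27 practice means and the other from about 1,350 patients. The training workshop, the tool and the documentation routine all reach patients through their practice, so patients of one practice are likely to change together. A patient-level paired t-test treats them as independent and understates the standard error. In a study without a control group, the confidence interval around the mean change is the main result, so its width matters.

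A smaller matter is that section 3.1 presents more than 50 patients per practice as a consequence of SD 15. A reader who cannot reproduce it cannot tell whether practices with fewer patients weaken the primary result.

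**Working it through.** **Inputs from the plan.** Difference 10 points; significance level 0.05; power 80%; 27 centres; 10% dropout; score SD 15, read here as the spread between patients within a practice; about 50 patients per practice.

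**Assumed, because the plan does not give them.** Correlation ρ between a patient's baseline and 12-month scores, shown from 0 to 0.8; between-practice SD of true change τ, shown at 2 and 5 points; two-sided testing unless stated.

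**The plan's own figures.**
- Dropout: 27 / 0.9 = 30, which reproduces.
- 27 centres: an exact paired t-test for 10 points at 80% power needs 27 pairs if the SD of change is about 17.5–17.8 (two-sided) or 20.0–20.3 (one-sided). The plan states neither an SD of change nor the sidedness, so 27 can be matched but not traced.
- The match does not settle the unit. SD 15 with ρ = 0.3 gives an SD of change of 15 × √(2 × 0.7) = 17.75, which also needs 27 pairs, and that is a patient-level quantity.

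**Effect of ignoring practice.** With m = 50 and 27 practices:
- within-practice SD of change: s = 15 × √(2(1 − ρ)), which is 21.2, 15.0 and 9.5 at ρ = 0, 0.5 and 0.8
- intraclass correlation of change: ICC = τ² / (τ² + s²)
- design effect: DE = 1 + 49 × ICC
- false-positive rate of the patient-level test: 2 × [1 − Φ(1.96 / √DE)]
- 95% half-width, patients: 1.96 × √((τ² + s²) / 1,350)
- 95% half-width, practice means: 2.056 × √((τ² + s²/50) / 27)

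| τ | ρ | ICC | DE | False-positive rate | Half-width, patients | Half-width, practices |
|---|---|---|---|---|---|---|
| 2 | 0 | 0.009 | 1.43 | 0.10 | 1.14 | 1.43 |
| 2 | 0.5 | 0.017 | 1.86 | 0.15 | 0.81 | 1.15 |
| 2 | 0.8 | 0.043 | 3.09 | 0.26 | 0.52 | 0.95 |
| 5 | 0 | 0.053 | 3.58 | 0.30 | 1.16 | 2.31 |
| 5 | 0.5 | 0.100 | 5.90 | 0.42 | 0.84 | 2.15 |
| 5 | 0.8 | 0.217 | 11.65 | 0.57 | 0.57 | 2.05 |

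With τ = 0 the rate is 0.05, so the inflation comes entirely from practices differing in true change.

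**Power if the SD of change is larger.** With an SD of practice-level change of 20, a two-sided test on 27 practices has 71% power and 34 are needed for 80%. One-sided, 27 practices give 81%.

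**Patients per practice.** Suppose that a single practice had to show 10 points at 80% power by itself. With SD 15, the paired t-test needs 38, 27, 20 or 10 patients at ρ = 0, 0.3, 0.5 or 0.8 (one-sided 30, 21, 16 or 8). None of these reaches 50.

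**The case against.** **The unit can be read from context.** Sections 2.4 and 3.1 count centres, dropout is applied to centres, and section 3.3 puts the collective above the individual. This favours the practice as the unit. But the same section 3.3 ties the primary endpoint to recording for each patient, and section 2.4 does not choose. The gap is narrower than total silence, but it remains.

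**At the planned effect the unit hardly matters.** With τ = 5, 27 practice means have more than 99.9% power for 10 points, so either analysis would detect a gain of that size. This stands for detection. It does not rescue the interval, nor the test when the true change is small or nil.

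**The inflation assumes inference beyond these practices.** This also stands as a condition. The plan does not say so explicitly, although its aim of establishing the score in different practice infrastructures suggests it.

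**More than 50 may rest on another calculation.** Section 3.1 attaches 10 points and 80% power to the 27 centres, not to each practice. A precision target could give a similar number: a 95% half-width of 4 points at SD 15 needs (1.96 × 15 / 4)² = 54. So the supportable statement is that the basis is not shown and SD 15 alone does not supply it. Section 3.2 says "the practice receives an evaluation of its practice performance compared to the overall collective", a use for which patients per practice matter directly, but section 3.1 does not give it as the reason.

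**Conclusion.** The main point holds: the unit of the primary test and the handling of clustering are missing, and one analysis that the text permits gives intervals that are too narrow. The size depends on τ and ρ, neither of which is in the plan. At τ = 2 the two-sided false-positive rate is about 0.10–0.26, and at τ = 5 about 0.30–0.57. The condition is that practices differ in true change and the inference is to extend beyond them.

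The point on more than 50 patients is minor: the necessity does not follow from SD 15 alone.

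Three stronger readings are not supported:
- A reader might take the SD of about 17.5–17.8 that reproduces 27 as the spread between practices, and reach a false-positive rate of about 0.66–0.76. That holds only if 27 was itself derived on practice means. In that case the practice was already the intended unit, and the patient-level test was not the plan.
- A reader might conclude that the study is underpowered. The 71% figure applies only if the SD of change is 20 and the test is two-sided; the 20 in section 2.4 is unlabelled and not linked to 27.
- A reader might call 50 patients an arithmetic error. The 10–38 range answers a question about one practice alone, under an assumed correlation of 0.8 to 0, which the plan does not pose.

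**What to change.** In section 2.4, name the unit, for example: *The primary paired t-test uses one mean score change per practice, two-sided at 0.05.* A patient-level model of change with a practice random effect would also serve. State the SD of change behind 27 centres and its source. If that SD does not give 80% power with 27 practices, restate the power.

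In section 3.1, give the actual basis for more than 50 patients per practice, or call it a target instead of a necessity.

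The cost is two or three sentences and a wider confidence interval than a patient-level test would show: in the table above, about 1.0–2.3 points on practice means against 0.5–1.2 on patients. Whether the number of centres can stay as it is depends on the SD of change once it is stated.

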2. PROJECT OBJECTIVES, DESIGN AND STATISTICS

2.1 Hypothesis and primary objective

By implementing evidence-based measures (by means of score), the treatment quality (corresponds to an improvement of the score) of patients with diabetes mellitus type 2 in the "Real World Setting" can be improved within 12 months.

The score can be used in different practice infrastructures and does not result in differences in treatment quality.

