2.3 Project design

Prospective, non-randomised study without control group.

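### Section 3.1 sets no minimum time since diagnosis, so patients diagnosed during the retrospective baseline year can enter the paired comparison with a partly pre-diagnosis baseline

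*Combined protocol and SAP*

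**What the plan says.** Section 3.1 has two inclusion conditions. The first concerns the disease: patients "who have ever had HbA1c > 6.4% and/or are taking insulin and/or oral AD according to their patient dossier". The second concerns time in care: "AND are at least 9 months in treatment with the same physician (in group practice in the same practice". The matching exclusion is "Supervision <9 months in practice (change of practice, move, death, complete external supervision regarding DM, etc". None of these refers to the date of diagnosis, and none gives the date at which the 9 months are counted.

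Section 2.4 fixes the two observation periods. For the first: "A baseline documentation takes place retrospectively from the training/workshop for the past 12 months". For the second: "a second, prospective documentation of the treatment is done during the following 12 months". The primary analysis is "Comparison of score baseline vs. 12 months using paired t-test", with no adjustment for diabetes duration.

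Section 2.3 describes the design as "Prospective, non-randomised study without control group". Section 2.1 attributes the expected improvement to the score: "By implementing evidence-based measures (by means of score), the treatment quality (corresponds to an improvement of the score". The only selection bias that the plan discusses (section 3.3) concerns patients with psychosocial problems. No section says how to score a baseline year in which diabetes was known for only part of the time.

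**The concern.** The paired comparison assumes that both 12-month periods measure the same thing: the quality of care of a patient known to have type 2 diabetes. For someone diagnosed inside the baseline window this fails. Diabetes checks were not due, and diabetes treatment was not expected, before the diagnosis.

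Take a long-standing patient of the practice whose first raised HbA1c came a few weeks before the workshop. On the wording of section 3.1 this patient is eligible. The baseline year is almost all pre-diagnosis, and the follow-up year is almost exactly the first year of known disease, when initial checks and treatment would be expected under usual care. The resulting rise in score owes nothing to the project, but a single-group before-after design has no means of separating it from the effect of the score.

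At stake is the size of the primary estimate, and possibly its significance, depending on the unit of analysis.

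**Working it through.** **The plan's own figure.** Sections 2.4 and 3.1 state 27 centres for a 10-point gain (56 to 66) at alpha 0.05 and 80% power. A spread of 20 (section 2.4, read as 58 ± 20), a one-sided paired test and n = (SD × (z_alpha + z_power) / delta)² give 24.7, so 25. The exact t calculation gives 27, with power 0.81. Two-sided with SD 20, the exact figure is 34. Inflating for dropout, 27 / 0.9 = 30, as stated. This point does not dispute the 27; it supplies the 10-point yardstick.

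**Who can enter.** The baseline window is the 12 months before the workshop.

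- Literal reading (9 months with the practice for any reason): a diagnosis at any time in the window is admissible, with up to about 12 pre-diagnosis months.
- Strict reading (9 months of diabetes treatment, counted at the workshop): only diagnoses in the first 12 − 9 = 3 months of the window are admissible, with at most 3 pre-diagnosis months.

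The gap is therefore open on both readings, but its width differs greatly. If the 9 months were counted at a date after the workshop, the strict reading would admit later diagnoses too.

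**Size.** The documents give no inputs for this, so all three are assumptions:

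- f, the share of patients diagnosed in the window: 4% to 8%.
- d, the score deficit of a fully pre-diagnosis year: 20 to 40 points.
- The deficit is proportional to the pre-diagnosis fraction p of the baseline year, and diagnoses are evenly spread.

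Bias in mean change = f × d × p.

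| Case | f | p | Low | High |
|---|---|---|---|---|
| Literal, even spread | 4-8% | 6/12 | 0.04 × 20 × 0.5 = 0.4 | 0.08 × 40 × 0.5 = 1.6 |
| Literal, all diagnosed just before the workshop | 4-8% | 1 | 0.04 × 20 = 0.8 | 0.08 × 40 = 3.2 |
| Strict, even spread | 1-2% (3/12 of 4-8%) | 1.5/12 | 0.01 × 20 × 0.125 = 0.025 | 0.02 × 40 × 0.125 = 0.10 |

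**Direction.** The formula takes the deficit as positive. For a diagnosis early in the window, the initial work-up falls inside the baseline year and may raise it. If the net extra gain of new patients were −10 points at a share of 10% (again assumed), the bias would be 0.10 × (−10) = −1.0 point.

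**Could it produce the whole 10 points?** Even with fully pre-diagnosis baselines, the share would have to be 10/40 = 25% at a 40-point deficit, or 10/20 = 50% at 20 points.

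**Against the standard error.** Section 2.4 does not name the unit of the paired test. Assume an SD of change of 20 and no clustering. With 27 centres the standard error is 20/√27 = 3.8. With 27 × 50 = 1,350 patients it is 20/√1350 = 0.54, and 1.96 × 0.54 = about 1.1 points would be significant at two-sided 0.05. In a patient-level test, the upper part of the 0.4-1.6 range could thus reach significance alone; in a centre-level test it could not.

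**The case against.** The strongest reply is that the 9 months were meant as diabetes care. The exclusion lists complete outside management of diabetes among its reasons, so a patient registered for 20 years but treated elsewhere for diabetes fails it. Section 3.4 likewise ends participation when a diabetologist takes over care completely. The inclusion rule also speaks of treatment and is joined to the disease definition. This reading is plausible, and on it the bias is negligible if the count is made at the workshop. It stands as an alternative, but the text does not settle it: the rule is worded by physician and practice, and no counting date is given.

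A second reply also stands in part. The score items and weights are not listed in the documents, so a 20-40 point deficit has no basis there. Section 1 names influenza vaccination, antihypertensives and statins among what is recorded, and none of these requires a diabetes diagnosis. A deficit of 40 is 40/15 = 2.7 times the within-practice SD in section 3.1. The deficit may well be smaller.

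Third, dating diagnosis by the first dossier entry could misclassify long-standing patients who joined the practice recently without their earlier records, and removing patients narrows the stated aim of documenting all eligible patients. Both objections are fair, and the fix has to allow for them.

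A reader might also infer that the error always favours the score, or that it distorts the comparison of practice forms. The documents support neither. The sign depends on when in the window the diagnosis falls, and nothing indicates that the share of new diagnoses differs between practice forms.

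**Conclusion.** The gap holds: nothing in the plan keeps patients diagnosed during the baseline year out of the primary paired comparison, and neither the design nor the analysis removes their first-year course from the result. The likely direction is upward for late-window diagnoses and uncertain for early ones.

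The size is modest and rests wholly on the assumptions listed above. The literal-reading range is 4% to 16% of the 10-point goal, and 32% in the extreme case; on the strict reading it is 1% or less. It would be wrong to conclude that new diagnoses could by themselves produce the targeted improvement, since the shares required are far above those assumed. The point is worth acting on because the bias is avoidable at little cost in a design with no other protection against it, not because it overturns the study.

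**What to change.** In section 3.1:

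1. State whether the 9 months mean diabetes treatment or any care in the practice, and the date at which they are counted.
2. Record the date of diagnosis as the earliest of: first HbA1c above the plan's threshold, first antidiabetic prescription, or an earlier diagnosis documented or reported by the physician. The last item protects patients whose old records were not transferred.
3. Limit the primary paired comparison to patients diagnosed on or before the start of the baseline window (workshop date minus 12 months).
4. Keep patients diagnosed within the window in the project and report them separately. Give the all-patient paired comparison as a prespecified sensitivity analysis, so that the real-world result remains visible.

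The cost is one extra date field in the recording tool, filled from a dossier that is already opened to check eligibility, and a short wording change. The primary comparison loses a few percent of patients: at the assumed 4-8%, that is 2 to 4 of every 50 per practice.
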